### 6.2.3.2 Handling

Infusion solutions should be prepared in **0.9% Sodium Chloride Injection, USP** (normal saline) or **5% Dextrose Injection, USP** (5% dextrose) and the final concentration of pembrolizumab in the infusion solutions should be between 1.0 mg/mL and 10.0 mg/mL. Please note, the preferred diluent is **0.9% Sodium Chloride** and **5% dextrose** is only permissible if normal saline is not available. Pembrolizumab should **NOT** be mixed with other diluents unless instructed by the MSD in writing. Parenteral drug products should be inspected visually for particulate matter and discoloration prior to administration. Discard the drug product vial if extraneous particulate matter other than translucent to white proteinaceous particles is observed.

Sites should follow their SOPs for drug transport and delivery, with all possible effort to minimise agitation of the reconstituted drug product between the pharmacy and the clinic.

#### **PLEASE DO NOT:**

- **Use if discoloration is observed.**
- **Shake or freeze the vial(s).**
- **Administer the product as an (intravenous (iv) push or bolus).**
- **Combine, dilute or administer it as an infusion with other medicinal products.**
- **Co-administer other drugs through the same infusion line.**

Further details on the preparation of the drug product can be found in the RM CTU pharmacy manual. At each site the Principle Investigator/designee e.g. pharmacist at each participating site is responsible for ensuring that all trial Medication must be stored in a secure, limited-access location under the storage conditions specified on the label. Receipt and dispensing of trial medication must be recorded by an

authorized person at the trial site. Trial medication may not be used for any purpose other than that stated in the protocol.

#### **6.2.4 Packaging and Labelling Information**

Pembrolizumab will be supplied by MSD as solution for injection. Pembrolizumab will be packaged, labelled and delivered to the participating sites free of charge by MSD. The IMP will be supplied specifically for the trial and should not be used for any other purpose than that stated in this protocol. The drug will be labelled in accordance to Good Manufacturing Practice Annex 13.

#### **6.2.5 Returns and Reconciliation**

The Principle Investigator/designees is responsible for keeping accurate accountability accurate records for pembrolizumab including the amount dispensed to and returned for each patient and the amount remaining on site at the conclusion of the trial. Upon completion or termination of the study, all unused and/or partially used trial medication will be destroyed at the site per institutional policy. It is the Principle Investigator's/designees responsibility to arrange for disposal of all empty containers, provided that procedures for proper disposal have been established according to applicable federal, state, local and institutional guidelines and procedures, and provided that appropriate records of disposal are kept.

#### **6.2.6 Doses and Treatment Regimens**

All patients will receive pembrolizumab administered as per standard procedures following manufacturer's instructions. Trial treatment should begin on the day of confirmation of eligibility or as close as possible to the date on which treatment is allocated/assigned.

**Table 7:** Pembrolizumab and lung SBRT schedules

Dose level	Lung SBRT Dose	Drug	Dose Frequency	Route of Administration	Dose
1	30 Gy in 3#	Pembrolizumab	3 weekly	IV infusion	200 mg
2	54 Gy in 3#	Pembrolizumab	3 weekly	IV infusion	200 mg
Expansion cohort	RP2D	Pembrolizumab	3 weekly	IV infusion	200 mg

#### **6.2.7 Timing of Dose Administration**

During the induction and maintenance phase, the pembrolizumab should be administered on Day 1 of each cycle after all procedures/assessments have been completed as detailed on the schedule of study assessments (Table 3). The pembrolizumab administration may be administered up to 3 days before or after the scheduled Day 1 during the induction and maintenance phase due to administrative reasons. During the

induction and maintenance phase of the trial, the pembrolizumab will be administered on a 3 weekly cycle (Table 3).

Maintenance pembrolizumab will continue until disease progression, withdrawal of consent, or unacceptable toxicity. Patients obtaining complete response or having completed 24 months of pembrolizumab have the option of discontinuing treatment, with a view to restarting treatment on disease progression. Retreatment should be discussed with the Chief Investigator. Study related assessment and procedures should be as for the beyond DLT Pembrolizumab Maintenance phase (see Table 3). Patients do not need to re-sign the consent form for restarting treatment, provided their consent is on the most up-to-date version of the Patient Information Sheet Consent Form.

All trial treatments will be administered on an outpatient basis. Pembrolizumab will be administered as a 30 minute IV infusion (treatment cycle intervals or infusion length may be increased due to toxicity as described in Section 6.2.3). Sites should make every effort to target infusion timing to be as close to 30 minutes as possible. However, given the variability of infusion pumps from site to site, a window of -5 minutes and +10 minutes is permitted (i.e., infusion time is 30 minutes: -5 min/+10 min). The RM CTU Pharmacy Manual contains specific instructions for pembrolizumab, reconstitution, preparation of the infusion fluid, and administration. In addition, infusion length may be increased due to toxicity as described in Section 7 and Table 9.

The RM CTU pharmacy manual contains specific instructions for pembrolizumab reconstitution, preparation of the infusion, and administration.

### **6.2.8 Blinding/Masking**

This is an open-label trial; therefore, the Sponsor, Investigator and patient will know the treatment administered.

### **6.2.9 Drug Dose Selection/Modification**

#### **6.2.9.1 Dose Selection**

Pembrolizumab is being given using standard 200 mg flat dosing every three weeks. The Pembrolizumab dosing interval may be increased due to toxicity as described in Section 3.1.1. Details on the preparation and administration of pembrolizumab are provided in the RM CTU Pharmacy Manual. These guidelines contain specific instructions for pembrolizumab reconstitution, preparation of the infusion fluid and administration.

### 6.2.9.2 Dose Modification

Pembrolizumab will be withheld for drug-related Grade 4 haematological toxicities, and non-haematological toxicity  $\geq$  Grade 3 including laboratory abnormalities, and severe or life-threatening AEs as per Table 8 below.

In case toxicity does not resolve to Grade 0-1 within 12 weeks after last infusion, trial treatment should be discontinued after consultation with the Sponsor. With Investigator and Sponsor agreement, patients with a laboratory AE still at Grade 2 after 12 weeks may continue treatment in the trial only if asymptomatic and controlled. For information on the management of AEs, see Section 7 and Table 8. Patients who experience a recurrence of the same severe or life-threatening event at the same grade or greater with re-challenge of pembrolizumab should be discontinued from trial treatment.

Events of Clinical interest (ECI) can be potential irAEs and dose modifications for these toxicities should they occur can be found in Appendix 5 and as per the MSD guidance document for pembrolizumab ECI version 3.0.

Dosing interruptions are permitted in the case of medical / surgical events or logistical reasons not related to study therapy (e.g., elective surgery, unrelated medical events, patient vacation, and/or holidays). Subjects should be placed back on study therapy within 3 weeks of the scheduled interruption, unless otherwise discussed with the Sponsor. The reason for interruption should be documented in the patient's study record.

**Table 8:** Dose modification guidelines for drug-related adverse events.

Toxicity	Hold Treatment For Grade	Timing for Restarting Treatment	Treatment Discontinuation
Diarrhoea/Colitis	2-3	Toxicity resolves to Grade 0-1.	Toxicity does not resolve within 12 weeks of last dose or inability to reduce corticosteroid to 10 mg or less of prednisone or equivalent per day within 12 weeks.
	4	Permanently discontinue	Permanently discontinue
AST, ALT, or Increased Bilirubin	2	Toxicity resolves to Grade 0-1	Toxicity does not resolve within 12 weeks of last dose.
	3-4	Permanently discontinue (see exception below) 	Permanently discontinue
Type 1 diabetes mellitus (if new onset) or Hyperglycemia	T1DM or 3-4	Hold pembrolizumab for new onset Type 1 diabetes mellitus or Grade 3-4 hyperglycemia associated with evidence of beta cell failure.	Resume pembrolizumab when patients are clinically and metabolically stable.
Hypophysitis	2-4	Toxicity resolves to Grade 0-1. Therapy with pembrolizumab can be continued while endocrine replacement therapy is instituted	Toxicity does not resolve within 12 weeks of last dose or inability to reduce corticosteroid to 10 mg or less of prednisone or equivalent per day within 12 weeks.
Hyperthyroidism	3	Toxicity resolves to Grade 0-1	Toxicity does not resolve within 12 weeks of last dose or inability to reduce corticosteroid to 10 mg or less of prednisone or equivalent per day within 12 weeks.
	4	Permanently discontinue	Permanently discontinue
Hypothyroidism		Therapy with pembrolizumab can be continued while thyroid replacement therapy is instituted	Therapy with pembrolizumab can be continued while thyroid replacement therapy is instituted.
Infusion Reaction	3-4	Permanently discontinue	Permanently discontinue
Pneumonitis	2	Toxicity resolves to Grade 0-1. If recurrent Grade 2 pneumonitis occurs pembrolizumab should be permanently discontinued.	Toxicity does not resolve within 12 weeks of last dose or inability to reduce corticosteroid to 10 mg or less of prednisone or equivalent per day within 12 weeks.
	3-4	Permanently discontinue	Permanently discontinue
Renal Failure or Nephritis	2	Toxicity resolves to Grade 0-1	Toxicity does not resolve within 12 weeks of last dose or inability to reduce corticosteroid to 10 mg or less of prednisone or equivalent per day within 12 weeks.
	3-4	Permanently discontinue	Permanently discontinue
All Other Drug-Related Toxicity 	3 or Severe	Toxicity resolves to Grade 0-1	Toxicity does not resolve within 12 weeks of last dose or inability to reduce corticosteroid to 10 mg or less of prednisone or equivalent per day within 12 weeks.
	4	Permanently discontinue	Permanently discontinue

**Note: Permanently discontinue for any severe or Grade 3 drug-related AE that recurs or any life-threatening event.**

 For patients with liver metastasis who begin treatment with Grade 2 AST or ALT, if AST or ALT increases by greater than or equal to 50% relative to baseline and lasts for at least 1 week then patients should be discontinued.

 Patients with intolerable or persistent Grade 2 drug-related AE may hold study medication at physician discretion.

Permanently discontinue study drug for persistent Grade 2 adverse reactions for which treatment with study drug has been held, that do not recover to Grade 0-1 within 12 weeks of the last dose.

## 6.3 Concomitant medications

Concomitant medications will be recorded at screening and at every visit during the treatment phase of the study in the case report form (CRF) in the concomitant therapy section.

### 6.3.1 Prohibited Concomitant Medications

Medications or vaccinations specifically prohibited in the exclusion criteria are also not allowed during the ongoing trial. If there is a clinical indication for one of these or other prohibited medications or vaccinations then the patient may be discontinued from trial therapy. The Investigator should discuss any questions regarding this with the chief investigator (or delegate).

The final decision on any supportive therapy or vaccination rests with the Investigator and/or the patient's primary physician. However, the decision to continue the patient on trial therapy or vaccination schedule requires the mutual agreement of the Chief Investigator, and the patient.

Patients are prohibited from receiving the following therapies during the Screening and Treatment Phase of this trial:

- Anti-cancer systemic chemotherapy or biological therapy
- Immunotherapy not specified in this protocol
- Investigational agents other than pembrolizumab
- Live vaccines within 30 days prior to the first dose of trial treatment and while participating in the trial. Examples of live vaccines include, but are not limited to, the following: measles, mumps, rubella, chicken pox, yellow fever, rabies, BCG, and typhoid (oral) vaccine. Seasonal influenza vaccines for injection are generally killed virus vaccines and are allowed; however intra-nasal influenza vaccines (e.g. Flu-Mist®) are live attenuated vaccines, and are not allowed.
- Glucocorticoids for any purpose other than to modulate symptoms from an event of clinical interest of suspected immunologic aetiology. The use of physiologic doses of corticosteroids may be approved after consultation with the Chief Investigator or delegate.
- Radiation therapy not specified in this protocol
  - Note: Subsequent radiotherapy whilst on maintenance treatment to the thorax will not be permitted. Radiation therapy to a symptomatic solitary lesion or to the brain may be allowed after consultation with the chief investigator, as long as it does not involve re-irradiation to any part of the lung.

Patients who in the assessment by the investigator, require the use of any of the aforementioned for their clinical management should be removed from the trial. Patients may receive other medications that the investigator deems to be medically necessary. The Exclusion Criteria describes other medications which are prohibited in this trial. There are no prohibited therapies during the Post-Treatment Follow-up Phase.

### 6.3.2 Acceptable Concomitant Medications

All treatments that the Investigator considers necessary for a patient's welfare may be administered at the discretion of the Investigator in keeping with the community standards of medical care. All concomitant medication will be recorded on the case report form (CRF) including all prescriptions, over-the-counter (OTC), herbal supplements, and IV medications and fluids. If changes occur during the trial period, documentation of drug dosage, frequency, route, and date may also be included on the CRF.

All concomitant medications received within 28 days before the first dose of trial treatment and 30 days after the last dose of trial treatment or initiation of other anti-cancer therapies should be recorded. Concomitant medications administered after 30 days after the last dose of trial treatment should only be recorded for SAEs and overdose and liver toxicity ECIs as defined in Section 7.

## 6.4 Rescue Medications & Supportive Care

### 6.4.1 Supportive Care Guidelines

Patients should receive appropriate supportive care measures as deemed necessary by the treating investigator including but not limited to the items outlined below:

#### 6.4.1.1 Diarrhoea

Patients should be carefully monitored for signs and symptoms of:

- Enterocolitis (diarrhoea, abdominal pain, blood or mucus in stool, with or without fever)
- Bowel perforation (peritoneal signs and ileus).

In symptomatic patients, infectious aetiologies should be ruled out, and if symptoms are persistent and/or severe, endoscopic evaluation should be considered.

- In patients with severe enterocolitis (Grade 3):
  - Pembrolizumab will be **permanently discontinued** and treatment with systemic corticosteroids should be initiated at a dose of 1 to 2 mg/kg/day of prednisone or equivalent. When symptoms improve to Grade 1 or less, corticosteroid taper should be started and continued over at least 1 month.
- In patients with moderate enterocolitis (Grade 2):
  - Pembrolizumab should be **withheld** and anti-diarrhoeal treatment should be started. If symptoms are persistent for more than one week, systemic corticosteroids should be initiated (e.g., 0.5 mg/kg/day of prednisone or equivalent). If symptoms are not improving within 48 hours of starting steroids for grade 3 enterocolitis, consider infliximab. When symptoms improve to Grade 1 or less, corticosteroid taper should be started and continued over at least 1

month. Guidelines for continuing treatment with pembrolizumab can be found in Appendix 5.

All patients who experience diarrhoea should be advised to drink liberal quantities of clear fluids. If sufficient oral fluid intake is not feasible, fluid and electrolytes should be substituted via i.v. infusion.

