#### *Immune-mediated colitis*

Monitor subjects for signs and symptoms of colitis and exclude other causes of colitis. Administer corticosteroids for Grade 2 (if persists for >3 days) or greater events (initial dose of 1-2 mg/kg/day prednisone or equivalent followed by a taper), withhold pembrolizumab for moderate (Grade 2) or severe (Grade 3) colitis, and permanently discontinue pembrolizumab for life-threatening (Grade 4) colitis.

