		
 
Report overdose and liver toxicity ECIs within 24 hours
 
Withhold pembrolizumab, may restart if Grade 1 or resolved within 12 weeks
 
Symptomatic treatment 
 
Consider GI consult & endoscopy to rule out colitis
 
 
 
	
 
Prednisone 1-2mg/kg/day or equivalent
 
Symptoms grade 1 or less, initiate steroid taper for no less than 4 weeks.
 
Permanently discontinue pembrolizumab if dose cannot be reduced to 10mg or less of prednisone or equivalent per days within 12 weeks.
 
If symptoms worsen or persist >1 week treat as grade 3.
 

		
 
• Report overdose and liver toxicity ECIs within 24 hours
 
• Withhold pembrolizumab
 
• Rule out bowel perforation
 
• Recommend gastroenterologist consult & biopsy with endoscopy
 
	
 
• methylprednisolone 125mg IV followed by prednisone 1 to 2 mg/kg/day or dexamethasone 4mg every 4 hours.
 
• Symptoms grade 1 or less initiate steroid taper for no less than 4 weeks.
 
• Taper 6-8 weeks in patients with diffuse or severe ulceration and/or bleeding
 
• If IV steroids do not reduce initial symptoms within 48-72 hours treat with additional anti-inflammatory measures. At symptom relief discontinue anti-inflammatory and initiate steroid taper over 45-60 days. If symptoms worsen during this period refer to Section 6 and 7.
 

			
 
• Manage as per grade 3
 

Endocrine – Hypo and hyperthyroidism	Grade 1 (Asymptomatic)	
 
• No action
 
	
 
• Intervention not indicated
 

	Grade 2 Hyperthyroidism and Grade 2- 4 Hypothyroidism	
 
• Report overdose and liver toxicity ECIs - see Section 6 and 7.
 
• Monitor thyroid function until returned to baseline.
 
• Consider consultation with endocrinologist.
 
• Pembrolizumab can continue while on this treatment.
 
	
 
• Thyroid hormone and/or steroid replacement therapy.
 
• Hyper – non-selective beta blockers for initial therapy
 
• Hypo – thyroid hormone replacement therapy as per standard of care.
 

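### For a first Grade 3 colitis that recovers, section 6.4.1.1 rules out further pembrolizumab while Table 8 allows a restart, and no order of precedence is given

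*Combined protocol and SAP*

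**What the plan says.** Four places set the handling of pembrolizumab after Grade 3 diarrhoea, colitis or enterocolitis.

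- **Section 6.4.1.1 (Diarrhoea).** Under the line "In patients with severe enterocolitis (Grade 3", the instruction is: "Pembrolizumab will be permanently discontinued and treatment with systemic corticosteroids should be initiated". The Grade 2 bullet that follows withholds the drug and ends with a pointer: "Guidelines for continuing treatment with pembrolizumab can be found in Appendix 5".
- **Section 6.2.9.2, Table 8.** The row reads "Diarrhoea/Colitis 2-3 Toxicity resolves to Grade 0-1", under column headings for the grade at which to hold and the timing of restart. The discontinuation column for that row begins: "Toxicity does not resolve within 12 weeks of last dose or inability to reduce corticosteroid to 10 mg or less of prednisone". Grade 4 has its own line and is permanent. A note under the table adds: "Permanently discontinue for any severe or Grade 3 drug-related AE that recurs or any life-threatening event".
- **Section 6.5 (immune-mediated colitis).** The instruction is to "withhold pembrolizumab for moderate (Grade 2) or severe (Grade 3) colitis, and permanently discontinue pembrolizumab for life-threatening (Grade 4) colitis".
- **Appendix 5 (colitis).** The row containing "Rule out bowel perforation" tells the investigator to withhold pembrolizumab. It has no sentence on restarting.

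**The concern.** Whether a patient may be given pembrolizumab again after a severe immune toxicity is a safety rule, and an investigator should find one answer to it. As written, an investigator who restarts under Table 8 departs from section 6.4.1.1, and one who stops for good under section 6.4.1.1 does not follow Table 8. Two patients with the same course could be managed differently, and either could be logged as a protocol deviation.

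Section 8.1 also plans to describe dose modifications, delays and duration of therapy. If like cases are handled under different rules, those summaries partly reflect which section the investigator read.

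**Working it through.** The plan gives no figure on this point to reproduce. The check is a comparison of the texts, followed by a small calculation of size.

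**1. Do the rules cover the same event?** Yes. Section 6.4.1.1 is headed Diarrhoea and speaks of enterocolitis. Table 8 has a joint diarrhoea and colitis row. Table 12 lists enterocolitis and diarrhoea under its colitis heading.

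**2. Side by side, for a first Grade 3 episode**

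| Place | At onset | After recovery to Grade 0-1 within 12 weeks, steroids reduced |
|---|---|---|
| 6.4.1.1 | Stop | No further drug |
| Table 8 | Hold | Restart allowed, stated explicitly |
| 6.5, colitis | Withhold | Not stated; implied by the contrast with Grade 4 |
| Appendix 5, third colitis row | Withhold | Not stated; the restart wording is in the row before |

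The grade labels of the Appendix 5 colitis rows are not legible in the text available. The third row is taken as Grade 3 because the row before says to treat worsening or persistent cases as Grade 3 and the row after says to manage as for Grade 3. The missing labels are not counted as a fault of the plan.

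**3. Where do the rules part?**
- Recurrent Grade 3: the Table 8 note also requires permanent discontinuation, so there is no conflict.
- Not resolved, or steroids not reduced, within 12 weeks: Table 8 also discontinues, so there is no conflict.
- Grade 4: Table 8 and section 6.5 both discontinue permanently.
- First Grade 3 episode that meets the 12-week conditions: section 6.4.1.1 forbids what Table 8 permits. This is the conflict.

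**4. Does another text settle it?** The Table 8 note does not, because it concerns recurrence or a life-threatening event. The pointer from section 6.4.1.1 to Appendix 5 sits in the Grade 2 bullet. Section 6.2.9.2 also sends the reader to Appendix 5 for modifications for events of clinical interest, and the Appendix 5 row does not carry section 6.4.1.1's permanent stop. Table 10 is left out of the comparison because section 6.5 limits it to events not detailed elsewhere in the protocol.

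**5. Size**
- One patient out of the maximum of 24 (section 3.2) is 1/24 = 4.2 percentage points of any discontinuation proportion.
- The documents state no colitis rate. Section 1.1.4.2 names only pneumonitis and severe skin reactions as grade 3-5 immune-related events reaching 1% in the docetaxel-controlled trial. If that list is complete, colitis of that severity was below 1% there. At a rate of 1%, the expected number is 24 × 0.01 = 0.24, and the chance of at least one case is 1 − 0.99^24 = 0.21. Both are upper figures for pembrolizumab alone, and the combination rate is unknown.

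**The case against.** The best defence is that the protocol has some structure. Section 6.2.9.2 is the dose-modification section and refers to Table 8. Section 6.4.1 is headed as supportive-care guidance and leaves measures to the treating investigator. Section 6.5 requires any immune-related event of Grade 2 or higher to be discussed at once with the Chief Investigator or delegate. Section 6.2.9.2 also cites a separate guidance document from the drug supplier, which is not available here. These points lower the risk but do not remove the conflict. The sentence in section 6.4.1.1 is a firm instruction on study drug, no text ranks it below Table 8, and a required discussion does not supply the rule to be applied.

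It is also fair to object that the texts are not opposites: all of them interrupt dosing at Grade 3. That stands, and it is why the point is confined to re-exposure.

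A reader might go further and infer that the conflict drives replacement and evaluability under section 4.3, for example if a patient on hold then progresses and is replaced while a patient taken off drug is counted. The documents do not support this. Section 4.3 turns on leaving the trial, not on stopping the drug, and sections 3.4.2 and 6.8.1 keep patients who stop pembrolizumab without progression in follow-up. Section 4.3's replacement for missing the 3-month follow-up excludes toxicity as the reason. A Grade 3 or higher non-haematological event at least possibly related to the combination, within the DLT period, falls under the DLT definition in section 3.2.1 whether the drug is held or stopped.

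**Conclusion.** The contradiction is real and in current text, and it should be corrected. It is limited to a first Grade 3 colitis or enterocolitis that recovers within Table 8's 12-week conditions. The firm clash is between section 6.4.1.1 on one side and Table 8 and section 6.5 on the other, with Appendix 5 as inferred support.

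Two stronger readings do not hold. One is that every Grade 3 case is affected: recurrent and non-resolving cases end in permanent discontinuation under Table 8 as well. The other is that three places promise a restart: only Table 8 says so in words.

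The consequences are for safety management and for the consistency of the section 8.1 treatment summaries. Few cases are likely in 24 patients, but each would be visible. Sample size, DLT counting and the primary endpoint are not shown to be affected. The conclusion assumes that enterocolitis and colitis are one category, as Table 12 has it, and that the third Appendix 5 colitis row is Grade 3. That three places withhold and one stops for good does not show which rule was intended.

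**What to change.** The sponsor, with the drug supplier, should decide which rule applies and reconcile section 6.4.1.1, Table 8, the colitis paragraph of section 6.5 and the Appendix 5 colitis rows to it. State the rule once, replace the other statements with cross-references, and say which text prevails if any difference remains. The rule should say explicitly whether re-exposure is possible after a first Grade 3 episode and, if so, under what conditions. The separate guidance document on events of clinical interest should be checked for agreement at the same time.

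The cost is protocol wording through the usual amendment route. The design, sample size and analysis plan do not change. If any Grade 3 case occurred before the correction, the report should say which section was followed.
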